 - v) Additional requirements for pregnancy testing during and after study intervention are located in [Section 2](#), Schedule of Assessments.
 - vi) The investigator is responsible for review of medical history, menstrual history, and recent sexual activity to decrease the risk for inclusion of a woman with an early undetected pregnancy.
 - vii) WOCBP must agree to follow instructions for method(s) of contraception defined in [Appendix 4](#) and as described below and included in the informed consent form.

- viii) WOCBP are permitted to use hormonal contraception methods (as described in [Appendix 4](#)).
- ix) A female participant is eligible to participate if she is not pregnant or breastfeeding, and at least one of the following conditions applies:
 - (1) Is not a WOCBP
 - OR
 - (2) Is a WOCBP and using one of the highly effective contraceptive methods as described in Appendix 4 for the duration of treatment with study drugs (BMS-986141, aspirin, ticagrelor) plus at least 5 half-lives of BMS-986141 (9 days, 5 half-lives of aspirin and ticagrelor are shorter than 9 days)

b) Male Participants

- i) Males, ages 18 to 75 years, inclusive.
- ii) Males who are sexually active with WOCBP must agree to follow instructions for method(s) of contraception defined in Appendix 4 and as described below.
- iii) Azoospermic males are exempt from contraceptive requirements.
- iv) No additional contraceptive measures are required to be used.

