In the case of pregnancy, the investigator must immediately, within 24 hours of awareness of the pregnancy, notify the BMS Medical Monitor/designee of this event. In most cases, the study treatment will be permanently discontinued in an appropriate manner (eg, dose tapering if necessary for participant safety). Refer to [Section 9.2.5](#) Pregnancy.

All participants who discontinue study treatment should comply with protocol-specified follow-up procedures as outlined in Section 2. The only exception to this requirement is when a participant withdraws consent for all study procedures including post-treatment study follow-up or loses the ability to consent freely (ie, is imprisoned or involuntarily incarcerated for the treatment of either a psychiatric or physical illness).

If study treatment is discontinued prior to the participant's completion of the study, the reason for the discontinuation must be documented in the participant's medical records and entered on the appropriate CRF page.

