9.2.4 Regulatory Reporting Requirements for SAEs

- Prompt notification by the investigator to the Sponsor of SAEs is essential so that legal obligations and ethical responsibilities towards the safety of participants and the safety of a product under clinical investigation are met.
- An investigator who receives an investigator safety report describing SAEs or other specific safety information (eg, summary or listing of SAEs) from the Sponsor will file it along with the Investigator's Brochure and will notify the IRB/IEC, if appropriate according to local requirements.

Sponsor or designee will be reporting adverse events to regulatory authorities and ethics committees according to local applicable laws including European Directive 2001/20/EC and FDA Code of Federal Regulations 21 CFR Parts 312 and 320. A SUSAR (Suspected, Unexpected Serious Adverse Reaction) is a subset of SAEs and will be reported to the appropriate regulatory authorities and investigators following local and global guidelines and requirements.

9.2.5 *Pregnancy*

If, following initiation of the study treatment, it is subsequently discovered that a participant is pregnant or may have been pregnant at the time of study exposure, including during at least for 5 half-lives (5 days) plus 30 days (duration of ovulatory cycle), for a total of 35 days after study product administration, the investigator must immediately notify the BMS Medical Monitor/designee of this event and complete and forward a Pregnancy Surveillance Form to BMS Designee within 24 hours of awareness of the event and in accordance with SAE reporting procedures described in [Appendix 3](#).

If the investigator determines a possible favorable benefit/risk ratio that warrants continuation of study treatment, or re-initiation of study treatment, a discussion between the investigator and the BMS Medical Monitor/designee must occur.

Follow-up information regarding the course of the pregnancy, including perinatal and neonatal outcome and, where applicable, offspring information, must be reported on the Pregnancy Surveillance Form.

Any pregnancy that occurs in a female partner of a male study participant should be reported to Sponsor or designee. In order for Sponsor or designee to collect any pregnancy surveillance information from the female partner, the female partner must sign an informed consent form for disclosure of this information. Information on this pregnancy will be collected on the Pregnancy Surveillance Form.

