Starting on Day 1, standard baseline photographs of any area with clinical findings will be taken at the discretion of the Principle Investigator. If there are any changes with the affected areas or new clinical findings, additional photographs will be obtained. Photographs will not be needed if there is no clinical finding or no change in the affected areas.

9.4.2 *Vital signs*

Refer to Schedule of Activities (Section 2).

9.4.3 *Electrocardiograms*

Refer to Schedule of Activities ([Section 2](#)).

9.4.4 *Clinical Safety Laboratory Assessments*

- Investigators must document their review of each laboratory safety report.
- A local laboratory will perform the analyses and will provide reference ranges for these tests.
- Results of clinical laboratory tests performed on Day 1 must be available prior to BMS-986141 dosing.

Hematology	
Red blood cells	
Hemoglobin	
Hematocrit	
Total leukocyte count, including differential	
Platelet count	
Chemistry	
AST	Total protein
ALT	Albumin
Total bilirubin	Sodium
Direct bilirubin	Potassium
Alkaline phosphatase	Chloride
Lactate dehydrogenase	Calcium
Creatinine	Phosphorus
Blood urea nitrogen	Magnesium
Uric acid	Creatine kinase
Fasting glucose	
Coagulation	
INR	
aPTT	
Prothrombin time	
Platelet count	
Urinalysis	
Protein	
Glucose	
Blood	
Leukocyte esterase	
Specific gravity	
pH	
Microscopic examination of the sediment if blood, protein or leukocytes esterase are positive on the dipstick	
Serology	

Serum for hepatitis C antibody, hepatitis B surface antigen, HIV-1 and -2 antibodies (screening only). See [Appendix 7](#) for hepatitis B serologic test results interpretation.

Other Analyses

Test for drugs of abuse and alcohol (urine or serum) (screening and Day 1)

Pregnancy test (WOCBP only: screening, predose, clinic discharge)

Follicle-stimulating hormone (postmenopausal women only; screening)

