
• a visit to the emergency room or other hospital department < 24 hours, that does not result in admission (unless considered an important medical or life-threatening event)• elective surgery, planned prior to signing consent• admissions as per protocol for a planned medical/surgical procedure• routine health assessment requiring admission for baseline/trending of health status (e.g., routine colonoscopy)• medical/surgical admission other than to remedy ill health and planned prior to entry into the study. Appropriate documentation is required in these cases• admission encountered for another life circumstance that carries no bearing on health status and requires no medical/surgical intervention (e.g., lack of housing, economic inadequacy, caregiver respite, family circumstances, administrative reason)• admission for administration of anticancer therapy in the absence of any other SAEs (applies to oncology protocols)
Results in persistent or significant disability/incapacity
Is a congenital anomaly/birth defect
Is an important medical event (defined as a medical event(s) that may not be immediately life-threatening or result in death or hospitalization but, based upon appropriate medical and scientific judgment, may jeopardize the participant or may require intervention [e.g., medical, surgical] to prevent one of the other serious outcomes listed in the definition above.) Examples of such events include, but are not limited to, intensive treatment in an emergency room or at home for allergic bronchospasm; blood dyscrasias or convulsions that do not result in hospitalization.) Potential drug induced liver injury (DILI) is also considered an important medical event. (See Section 9.2.7 for the definition of potential DILI.)

Pregnancy and potential drug induced liver injury (DILI) must follow the same transmission timing and processes to BMS as used for SAEs (see [Section 9.2.5](#) for reporting pregnancies).

Any component of a study endpoint that is considered related to study therapy should be reported as SAE (e.g., death is an endpoint, if death occurred due to anaphylaxis, anaphylaxis must be reported).

EVALUATING AES AND SAES

Assessment of Causality

- The investigator is obligated to assess the relationship between study intervention and each occurrence of each AE/SAE.

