- A “reasonable possibility” of a relationship conveys that there are facts, evidence, and/or arguments to suggest a causal relationship, rather than a relationship cannot be ruled out.
- The investigator will use clinical judgment to determine the relationship.
- Alternative causes, such as underlying disease(s), concomitant therapy, and other risk factors, as well as the temporal relationship of the event to study intervention administration will be considered and investigated.
- The investigator will also consult the Investigator’s Brochure (IB) and/or Product Information, for marketed products, in his/her assessment.
- For each AE/SAE, the investigator must document in the medical notes that he/she has reviewed the AE/SAE and has provided an assessment of causality.
- There may be situations in which an SAE has occurred and the investigator has minimal information to include in the initial report to Sponsor. However, it is very important that the investigator always make an assessment of causality for every event before the initial transmission of the SAE data to Sponsor.
- The investigator may change his/her opinion of causality in light of follow-up information and send a SAE follow-up report with the updated causality assessment.
- The causality assessment is one of the criteria used when determining regulatory reporting requirements.

Follow-up of AEs and SAEs

If only limited information is initially available, follow-up reports are required. (Note: Follow-up SAE reports must include the same investigator term(s) initially reported.)

If an ongoing SAE changes in its intensity or relationship to study treatment or if new information becomes available, the SAE report must be updated and submitted within 24 hours to BMS (or designee) using the same procedure used for transmitting the initial SAE report.

All SAEs must be followed to resolution or stabilization.

REPORTING OF SAEs TO SPONSOR OR DESIGNEE

- SAEs, whether related or not related to study treatment, and pregnancies must be reported to BMS (or designee) immediately within 24 hours of awareness of the event.
- SAEs must be recorded on the SAE Report Form.
 - The required method for SAE data reporting is through the eCRF.
 - The paper SAE Report Form is only intended as a back-up option when the electronic data capture (EDC) system is unavailable/not functioning for transmission of the eCRF to BMS (or designee).

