APPENDIX 4 WOMEN OF CHILDBEARING POTENTIAL DEFINITIONS AND METHODS OF CONTRACEPTION

DEFINITIONS

Woman of Childbearing Potential (WOCBP)

A woman is considered fertile following menarche and until becoming post-menopausal unless permanently sterile. Permanent sterilization methods include hysterectomy, bilateral salpingectomy, and bilateral oophorectomy.

Women in the following categories are not considered WOCBP

- Premenarchal
- Premenopausal female with 1 of the following:
 - Documented hysterectomy
 - Documented bilateral salpingectomy
 - Documented bilateral oophorectomy

Note: Documentation can come from the site personnel's review of the participant's medical records, medical examination, or medical history interview.

- Postmenopausal female
 - A postmenopausal state is defined as 12 months of amenorrhea in a woman over age 45 years in the absence of other biological or physiological causes. In addition, females under the age of 55 years must have a serum follicle stimulating hormone, (FSH) level > 40 mIU/mL to confirm menopause.

Note: Females treated with hormone replacement therapy, (HRT) are likely to have artificially suppressed FSH levels and may require a washout period in order to obtain a physiologic FSH level. The duration of the washout period is a function of the type of HRT used. The duration of the washout period below are suggested guidelines and the investigators should use their judgement in checking serum FSH levels.

- 1 week minimum for vaginal hormonal products (rings, creams, gels)
- 4 week minimum for transdermal products
- 8 week minimum for oral products

Other parenteral products may require washout periods as long as 6 months. If the serum FSH level is > 40 mIU/mL at any time during the washout period, the woman can be considered postmenopausal.

End of Relevant Systemic Exposure

- End of relevant systemic exposure is the time point where the IMP or any active major metabolites has decreased to a concentration that is no longer considered to be relevant for human teratogenicity or fetotoxicity. This should be evaluated in context of safety margins

from the no-observed adverse effect level (NOAEL) or the time required for 5 half-lives of the IMP to pass.

METHODS OF CONTRACEPTION

One of the highly effective methods of contraception listed below should be continued for a minimum of 9 days (5 half-lives of BMS-986141, 5 half-lives of aspirin and ticagrelor are shorter than 9 days) post-treatment completion.

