Guidance for collection of Pregnancy Information and outcome of pregnancy on the Pregnancy Surveillance Form is provided in [Section 9.2.5](#) and the Appendix for Adverse Events and Serious Adverse Events Definitions and procedures for Evaluating, Follow-up and Reporting

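### Section 9.2.5 counts five half-lives as 5 days and reaches a 35-day pregnancy window; Section 6.1 and Appendix 4 count five half-lives of BMS-986141 as 9 days, which gives 39

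*Combined protocol and SAP*

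**What the plan says.** Section 9.2.5 (Pregnancy) requires immediate notification, and a surveillance form within 24 hours of awareness, when a participant is found to be pregnant or possibly pregnant at the time of study exposure. It extends that exposure period to at least "5 half-lives (5 days) plus 30 days (duration of ovulatory cycle), for a total of 35 days after study product administration". It does not name the drug to which the half-lives belong.

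Two other places in current text state the same quantity for BMS-986141:

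- Section 6.1, criterion 3)a)ix)(2), requires contraception for the duration of study drug treatment "plus at least 5 half-lives of BMS-986141 (9 days, 5 half-lives of aspirin and ticagrelor are shorter than 9 days").
- Appendix 4, under methods of contraception, says that a highly effective method should be "continued for a minimum of 9 days (5 half-lives of BMS-986141"), and again notes that the other two drugs need less time.

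The sections are linked. Appendix 4 ends with a pointer: "Guidance for collection of Pregnancy Information and outcome of pregnancy on the Pregnancy Surveillance Form is provided in" Section 9.2.5. Section 8.1 and Appendix 3 also send the reader to Section 9.2.5 for pregnancies.

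**The concern.** Five half-lives of one drug cannot be both 5 and 9 days. A contraception period and a pregnancy-reporting period may properly differ in length, but here the difference in purpose is carried by the separate 30-day ovulatory-cycle term. The half-life term should be the same in both.

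The unnamed drug in Section 9.2.5 does not resolve this. By the protocol's own statement BMS-986141 has the longest five-half-life period of the three study drugs, and it is the only one given in all four arms. A window meant to cover study drug exposure must therefore be set by BMS-986141.

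At stake is whether the one numeric pregnancy window in the protocol covers what it says it covers: elimination of the drug plus one full ovulatory cycle.

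**Working it through.** **Inputs**

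| Quantity | Value | Source |
|---|---|---|
| Five half-lives, pregnancy window | 5 days | Section 9.2.5 |
| Ovulatory-cycle term | 30 days | Section 9.2.5 |
| Five half-lives of BMS-986141, contraception | 9 days | Section 6.1; Appendix 4 |
| Half-life labelled terminal | about 22 h | Section 3.2.3 |
| Half-life labelled terminal | about 40 h | Section 5.5 |
| Half-life labelled effective | about 22 h | Section 5.5 |

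**Step 1. The plan's own figure.** Window = five half-lives + 30 days = 5 + 30 = 35 days. The stated total is reproduced.

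**Step 2. The same formula with the 9 days stated elsewhere.** 9 + 30 = 39 days. The difference is 39 − 35 = 4 days.

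**Step 3. What 35 days leaves for the ovulatory cycle.** Counting both periods from the single BMS-986141 dose on Day 1, 35 − 9 = 26 days, against the 30 intended (4 short).

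The start points in the text are not quite the same. Section 9.2.5 counts from study product administration, while Appendix 4 counts from the end of treatment. In Arms 1 to 3 background drug is still given on Day 2. If the 9 days ran from then, about a day later, the remainder would be about 25 days. The shortfall does not go away.

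**Step 4. Where the two figures may come from (inference only).** The protocol does not give the source of either.

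- With 22 h: 5 × 22 / 24 = 4.58 days, which rounds up to 5 and gives 35.
- With 40 h: 5 × 40 / 24 = 8.33 days, which rounds up to 9 and gives 39.

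Both stated figures are what one gets by rounding up. This suggests that Section 9.2.5 used the 22 h value and the contraception text used the 40 h value. Sections 3.2.3 and 5.5 disagree on which of these is the terminal half-life. Amendment 02 aligned the contraception duration between Section 6.1 and Appendix 4. Its table of key changes does not list Section 9.2.5, but that table covers major changes only, so the omission proves nothing.

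**The case against.** The contradiction itself is hard to dispute. The case on the other side is that it has almost no consequence and that the direction of the correction is not settled by the protocol alone.

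- **It is a floor on the exposure period and sets no reporting cut-off.** The 35 days is worded as a minimum, and the reporting deadline is 24 hours from awareness. This stands, and it means one should not speak of a hard gap on days 36 to 39.
- **Other text already covers reporting.** Section 8.1 says that "the investigator must immediately, within 24 hours of awareness of the pregnancy, notify the BMS Medical Monitor/designee of this event", and Appendix 3 says that "pregnancies must be reported to BMS (or designee) immediately within 24 hours of awareness of the event"; neither sets a day limit. Appendix 3 adds: "Pregnancy and potential drug induced liver injury (DILI) must follow the same transmission timing and processes to BMS as used for SAEs". A pregnancy on day 37 that the investigator knows of would be reported on these rules. This stands.
- **Nothing is scheduled at either day.** Section 9.4.4 lists "Pregnancy test (WOCBP only: screening, predose, clinic discharge"), and the on-treatment schedules in Tables 2-2 and 2-3 mark a test on Day 1 only. The last planned contact is the telephone call on Day 8 (± 2 days). This stands.
- **Either half-life could be the intended one.** The protocol gives both 22 h and 40 h, and the Investigator's Brochure is needed to decide between them. This stands in part. The 9 days is stated twice, is attributed to BMS-986141 by name, agrees with the 40 h terminal half-life in Section 5.5 and is the more cautious value. It is the reasonable default, subject to the brochure check.

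These points limit the consequence. None of them makes 5 days and 9 days agree.

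**Conclusion.** The inconsistency is real and minor. Section 9.2.5 states 35 days where its own rule, with the protocol's stated five half-lives of BMS-986141, gives 39. The size is 4 days, or 26 instead of 30 days of ovulatory-cycle cover.

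This rests on two assumptions: that BMS-986141 governs the window, which follows from the protocol's statement that the other drugs' periods are shorter, and that 9 days is the correct figure, which the protocol states twice but which has not been checked against the brochure. If the brochure supported a different value, 39 would change, but the present text would still need correcting because the sections disagree.

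The contraception duration is 9 days in both places and is unaffected. So are dosing, the primary endpoint, the sample size and every planned analysis.

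**What to change.** In Section 9.2.5, change the half-life term from 5 to 9 days and the total from 35 to 39 days, and name BMS-986141 as the drug to which the half-lives refer.

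Before the text is finalised, ask the sponsor to reconcile the half-life statements in Sections 3.2.3 and 5.5 against the Investigator's Brochure. If the brochure supports a value other than 9 days for five half-lives, use that value in Sections 6.1 and 9.2.5 and in Appendix 4 together.

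The cost is one wording change in the next amendment and one document check. No visits, tests, participants or analyses are added.

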9.4.5 Imaging Safety Assessment

Not applicable.

9.5 Pharmacokinetics

Pharmacokinetic characteristics of BMS-986141, metabolite BMT-162856, ASA, salicylic acid, and ticagrelor will be observed from plasma concentration versus time data. Potential correlation between drug exposures and thrombus formation in an ex vivo porcine aortic thrombosis chamber and other biomarkers/PD markers will be explored. The PK samples being collected will provide concentrations near Tmax.

[Table 9.5-1](#) (Treatment Arm 1), [Table 9.5-2](#) (Treatment Arm 2), [Table 9.5-3](#) (Treatment Arm 3), and [Table 9.5-4](#) (Treatment Arm 4) list the sample schedule to be following for the PK assessments of BMS-986141, ticagrelor, and ASA.

Table 9.5-1: Pharmacokinetic Sampling Schedule for BMS-986141 and Ticagrelor (Treatment Arm 1)

Study Day of Sample Collection	Event	Time (Relative To BMS-986141 Dose)Hour: Min	BMS-986141 and BMT-162856 Blood Sample for Plasma PK Profiling	Ticagrelor Blood Sample for Plasma PK Profiling
1	predose ^a	-02:00	X	X
1		02:00	X	X
2		24:00	X	X

^a The predose sample should be collected within 2 hours prior to BMS-986141 administration.

Abbreviation: PK = pharmacokinetic

Table 9.5-2: Pharmacokinetic Sampling Schedule for BMS-986141 and Acetylsalicylic Acid (Treatment Arm 2)

Study Day of Sample Collection	Event	Time (Relative To BMS-986141 Dose)Hour: Min	BMS-986141 and BMT-162856 Blood Sample for Plasma PK Profiling	Acetylsalicylic Acid and Salicylic Acid Blood Sample for Plasma PK Profiling
1	predose ^a	-02:00	X	X
1		02:00	X	X
2		24:00	X	X

^a The predose sample should be collected within 2 hours prior to BMS-986141 administration.

Abbreviation: PK = pharmacokinetic

Table 9.5-3: Pharmacokinetic Sampling Schedule for BMS-986141, Ticagrelor, and Acetylsalicylic Acid (Treatment Arm 3)

Study Day of Sample Collection	Event	Time (Relative To BMS-986141 Dose)Hour: Min	BMS-986141 and BMT-162856 Blood Sample for Plasma PK Profiling	Ticagrelor Blood Sample for Plasma PK Profiling	Acetylsalicylic Acid and Salicylic Acid Blood Sample for Plasma PK Profiling
1	predose ^a	-02:00	X	X	X
1		02:00	X	X	X
2		24:00	X	X	X

^a The predose sample should be collected within 2 hours prior to BMS-986141 administration.

Abbreviation: PK = pharmacokinetic

Table 9.5-4: Pharmacokinetic Sampling Schedule for BMS-986141 (Treatment Arm 4)

Study Day of Sample Collection	Event	Time (Relative To BMS-986141 Dose)Hour: Min	BMS-986141 and BMT-162856 Blood Sample for Plasma PK Profiling
1	predose	00:00	X
1		02:00	X
2		24:00	X

Abbreviation: PK = pharmacokinetic

The plasma samples will be analyzed for BMS-986141, ASA, salicylic acid, and ticagrelor by validated liquid chromatography mass spectrometry/mass spectrometry (LC-MS/MS) assays. BMT-162856, a metabolite of BMS-986141, will be analyzed by a qualified LC-MS/MS assay. In addition, plasma samples will be archived for potential metabolite analysis, if the need arises and to the extent possible.

Detailed instructions for the PK blood collection, labeling, processing, storage, and shipping will be provided to the site in the procedure manual.

